## 11.4 Method of Analysis & Reporting

### 11.4.1 General Approach

Non-inferiority testing for the primary safety and efficacy endpoint will be one-sided and performed at a 0.025 significance level for the comparison of the BuMA DES arm with the DP EES arm. Superiority tests on the secondary powered endpoint of long-term safety and efficacy (if the primary non-inferiority endpoint is met) and the primary safety and efficacy endpoint (if the secondary superiority endpoint is met) will be performed at a two-sided 0.05 significance level.

Analysis of all additional safety and efficacy endpoint results will be summarized using descriptive statistics. For binary variables, descriptive statistics will include counts, percentages, and sample size for each treatment group; p-values may be presented for hypothesis-generating purposes. For continuous variables, descriptive statistics include mean, median, standard deviation, quartiles, minimum, maximum, and sample size for each treatment group. Binary variables will be summarized using frequencies, percentages, and sample size for each treatment group. For time-to-event data, Kaplan-Meier estimates at the indicated time points will be displayed graphically.

Analysis will be conducted using SAS (version 9.3 or greater), unless otherwise noted. Please refer to the formal Statistical Analysis Plan (SAP) for additional details.

### 11.4.2 Baseline Characteristics

The following data will be summarized using descriptive statistics and presented by treatment group for the ITT and PP populations:

- Baseline demographics
- Baseline comorbidities, risk factors, and medical history
- Cardiac risk factors, angina status, and cardiac history
- Procedural characteristics

- Device details

### 11.4.3 Primary Endpoint Analysis

The primary analysis will be a test for non-inferiority of the BuMA DES compared with DP EES for the primary endpoint of TLF at 12 months, performed in the Per Protocol (PP) and Intention to Treat (ITT) populations using the Farrington-Manning test. If non-inferiority for the primary endpoint is met and superiority for the powered secondary endpoint is met, formal superiority testing will be performed for the primary endpoint.

The primary endpoint will be evaluated in both the PP and ITT populations. For the primary analyses, only subjects who experienced a primary endpoint event or who had at least 11 months follow-up (1 year minus the allowable 30 day window) and who meet the applicable analysis population definition will be included in the analysis. Analysis is at the subject level. A subject will be considered a failure for TLF if the subject experiences a cardiac death, a target vessel-related myocardial infarction (TV-MI) in any target vessel, or clinically-driven target lesion revascularization (TLR) in any study target lesion.

As an additional analysis, to account for any missing data in the primary endpoint, a tipping point analysis will be conducted. A sensitivity analysis for the primary endpoint will also be conducted according to the pre-specified alternate biomarker thresholds for PCI-related MI (§17.1).

In addition, to assess the appropriateness of pooling results between study regions (North America vs. Japan vs. Europe), an assessment of the effect of region on the primary endpoint will be carried out in the PP and ITT populations using interaction testing from the logistic regression with a 0.15 level of significance. A non-significant result for region will support the pooling of patients across regions for the primary safety and efficacy analysis. A significant result will require further inspection of the by-region results to assess if poolability is appropriate.

### 11.4.4 Secondary Powered Endpoint Analysis

The powered secondary endpoint of long-term safety and efficacy, defined as TLF between 12 months and 5 years by landmark Kaplan-Meier analysis, will be a test for superiority of the BuMA DES group to the DP EES group via the log-rank test in the ITT population. Subjects who experience TLF prior to 12 months will be excluded from this analysis. The analysis will be performed when the last enrolled subject has completed his/her 5 year clinical follow-up visit, and will be performed only if non-inferiority for the primary endpoint has been met.

### 11.4.5 Additional Secondary Endpoints Analysis

#### 11.4.5.1 Secondary Safety Endpoints

All secondary safety endpoints will be evaluated in the ITT population using appropriate descriptive statistics. No formal hypothesis testing will be performed. Statistics for continuous variables will include mean, median, standard deviation, minimum, maximum, and sample size for each treatment group. Binary variables will be summarized using frequencies, percentages, and sample size for each treatment group.

As a secondary analysis, all secondary safety endpoints will be evaluated in the PP population.

#### 11.4.5.2 Secondary Efficacy Endpoints

All secondary efficacy endpoints will be evaluated in the ITT population using appropriate descriptive statistics. No formal hypothesis testing will be performed. Statistics for continuous variables will include mean, median, standard deviation, minimum, maximum, and sample size for each treatment group. Binary variables will be summarized using frequencies, percentages, and sample size for each treatment group.

As a secondary analysis, all secondary efficacy endpoints will be evaluated in the PP population.

### 11.4.6 Subgroup Analyses

Subgroup analyses will be performed for all primary and secondary endpoints in their respective primary analysis populations for the following subgroups, and results will be reported by treatment group using descriptive statistics:

- Enrollment region (North America vs. Japan vs. Europe)
- Presentation (stable coronary artery disease vs. acute coronary syndromes)
- Single- versus multi-vessel disease (1 vs. 2 target vessels)
- Diabetes status (subjects with vs. without medically-treated diabetes mellitus)
- Subject gender (male vs. female)

The interaction p-value for the subgroup by treatment effect will be presented.

### 11.4.7 Additional Analyses

The following data will be summarized using descriptive statistics presented by treatment group in the ITT and PP populations:

- Subject enrollment and data compliance by site and visit (data compliance at each visit is the percentage of patients whose data forms have been collected and entered divided by the percentage of patients whose forms should have been collected and entered)
- Frequency (number and percentage of patients) with each type of concomitant medication
- Frequency (number and percentage of patients) with each site-reported Treatment Emergent AE overall and by MedDRA system organ class and preferred term (a treatment emergent AE is an AE that started or worsened during or after the index procedure)
- Frequency (number and percent of patients) with each site-reported Treatment Emergent Serious AE overall and by MedDRA system organ class and preferred term
- Frequency (number and percent of patients) with each site-reported Treatment Emergent AE or SAE, by CEC-adjudicated relationship to the investigational device or procedure
- Protocol deviations (number and percentage of patients with each deviation type)
- Detailed listings on primary and secondary endpoints, site-reported AE, and protocol deviations

### 11.4.8 Handling of Multiplicity Issues

The primary safety and efficacy endpoint will be evaluated simultaneously in the co-primary PP and ITT populations, and trial success requires meeting the non-inferiority criterion in both analyses. Therefore, adjustment for Type I error is not necessary.

The secondary powered endpoint hypothesis will only be tested if the primary endpoint non-inferiority hypothesis is met. Superiority for the primary endpoint will be tested if the secondary powered endpoint hypothesis is confirmed.

### 11.4.9 Multicenter Studies

The appropriateness of pooling data across sites will be assessed by including a random effect for site in a random effects model assessing the primary endpoint using the logit link. If a test of the variance from the mixed effects model is significant at  $\alpha=0.15$ , then it will be determined that heterogeneity by site exists. If this occurs, the primary endpoint results will be presented by site and the final analysis will be stratified by site. Sites with less than 10 subjects will be pooled according to study region as defined previously.

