## 5.0 Study Design

### 5.1 Study Design Overview

This prospective, multicenter study will enroll up to 1632 subjects at up to 130 investigational sites in North America, Japan, and Europe. A minimum of 50% of subjects will be enrolled at North American sites, and no single center will be permitted to enroll more than 10% of all subjects.

Patients presenting with symptomatic ischemic heart disease (including chronic stable angina with evidence of ischemia, unstable angina, or non-ST segment elevation myocardial infarction) who require elective or urgent percutaneous coronary intervention (PCI) to treat up to 3 native coronary artery lesions in up to 2 major coronary arteries, in vessel diameters of  $\geq 2.25$  mm to  $\leq 4.00$  mm and lesion lengths  $\leq 31$  mm, and who meet all eligibility criteria will be enrolled in the study and randomized 2:1 (stratified by presentation [acute coronary syndrome vs. non-ACS], diabetes status [with vs. without medically-treated diabetes mellitus], and study site) to the following treatment groups:

- **Intervention:** Coronary revascularization with the BuMA Supreme Biodegradable Drug Coated Coronary Stent System (BuMA DES)
- **Control:** Coronary revascularization with the commercially-available durable polymer everolimus-eluting stent systems (DP EES)

Subjects will have clinical follow-up in-hospital and at 30 days, 6 months, 12 months\*, and 2, 3, 4, and 5 years. Follow-up at 30 days and 12 months will be clinic visits, while 6-month follow-up and annual follow-up at 2-5 years will be via telephone contact (or optional clinic visit). Subjects in whom no study stent is implanted will be followed to 12 months only. \*NOTE: For the duration of the Coronavirus Disease 2019 (COVID-19) pandemic, phone follow-up or virtual visit at 12 months is permitted if necessary to assure the safety of trial participants.

The primary analysis will be a non-inferiority test comparing BuMA DES to DP EES for the primary safety and efficacy endpoint of target lesion failure at 12 months in the Intention to Treat and Per Protocol patient populations. As a secondary hypothesis-driven analysis, a superiority test comparing BuMA DES to DP EES will be performed for the powered secondary endpoint of long-term safety and efficacy, defined as target lesion failure between 12 months and 5 years by landmark analysis. The study will also report additional secondary safety and efficacy endpoints.

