#### 5.5 Multicenter Studies

The appropriateness of pooling data across sites will be assessed using a logistic regression model including a random effect for site to test whether sites have a significant variability in the primary endpoint. If it's determined that heterogeneity by site exists, the primary endpoint results will be presented by site and the final analysis will be stratified by site. Sites with less than 10 subjects will be pooled according to study region as defined previously.

In addition, to assess the appropriateness of pooling results between study regions (North America vs. Japan vs. Europe), an assessment of the effect of region on the primary endpoint will be carried out in

	FORM	Document No BIO-TMP-0702 Revision: 00
	TITLE Statistical Analysis Plan	Effective date: 16-Mar-2018 Department: BIO

the PP and ITT populations using interaction testing between region and treatment effect from the logistic regression. A non-significant result for region will support the pooling of patients across regions for the primary safety and efficacy analysis. A significant result will require further inspection of the by-region results to assess if poolability is appropriate.

Both tests will be performed at a 15% level of significance level.

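### The site-pooling check tests whether sites differ in TLF risk, not whether the device effect differs between sites

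*Protocol*

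**What the plan says.** Protocol 11.4.9 sets out the site check: "The appropriateness of pooling data across sites will be assessed by including a random effect for site in a random effects model", using a logit link and the primary endpoint. The decision rule begins "If a test of the variance from the mixed effects model is significant at" 0.15, in which case heterogeneity by site is declared and "the primary endpoint results will be presented by site and the final analysis will be stratified by site". Small sites are handled first: "Sites with less than 10 subjects will be pooled according to study region as defined previously".

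SAP 5.5 keeps the random site effect and gives its purpose as "to test whether sites have a significant variability in the primary endpoint". It repeats the consequence and sets the level: "Both tests will be performed at a 15% level of significance level".

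For regions the question is different. SAP 5.5 assesses poolability "using interaction testing between region and treatment effect from the logistic regression", and Protocol 11.4.3 also calls for interaction testing. There, a significant result leads to closer inspection of the by-region results.

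Neither document names a treatment-by-site term or a random treatment slope. Protocol 11.4.9 does not say whether treatment is in the site model; adding it as a fixed effect would not change what the site variance measures.

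**The concern.** The variance of a random site intercept describes how much TLF risk differs between sites. Protocol 11.5.1 stratifies randomisation by site, so a site's underlying risk is unrelated to the arm a subject receives and does not bias the BuMA minus DP EES difference. Under the planning assumption of equal arm rates, the true difference is zero at every site, whatever its risk. Pooling becomes hard to interpret when the device effect varies by site, and the planned model does not isolate that.

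Two things are at stake. Ordinary differences in case mix could change the form of the final analysis. And a non-significant result could be taken as support for a consistent device effect, which it does not show.

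**Working it through.** **Inputs from the documents.** 1551 evaluable subjects (1034:517), 2:1 allocation, TLF 6.5% in both arms, margin 3.575%, one-sided alpha 0.025 (Protocol 11.3.1); up to 130 sites (Protocol 5.1); pooling tests at 0.15.

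**The plan's own figure.** With a true difference of zero, Farrington-Manning power is Φ[(Δ − z·s0)/s1], where s0 uses the rates restricted to differ by Δ (8.15% and 4.58%) and s1 uses 6.5% in both arms.
- s0 = √(0.0815×0.9185/1034 + 0.0458×0.9542/517) = 0.01252
- s1 = √(0.065×0.935/1034 + 0.065×0.935/517) = 0.01328
- Power = Φ[(0.03575 − 1.96×0.01252)/0.01328] = Φ(0.84) = 80.06%

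The stated size is reproduced: 517 controls, 1551 in total, is the smallest that gives 80%.

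**Information per site at 130 sites.** 1551/130 = 11.9 subjects; 11.9×0.065 = 0.78 TLF events; (517/130)×0.065 = 0.26 control events.

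**Simulation.** 4000 trials per setting, TLF 6.5% overall, 2:1. The layouts and SDs are assumptions: 130 sites of 12, 70 sites of 9 to 36, and 40 units of 39. Two stand-in tests were each set to the 15% level using 20,000 trials without heterogeneity:
- Site-variance score test (the planned question): Σ[(O − E)² − V] / √Σ2V², with O the site's TLF count and E, V from the overall arm rates.
- Treatment-by-site test: Σ[(y − E)² − V] / √ΣV², with y the BuMA events, E = M·n_I/N and V = M(N − M)n_I·n_C / [N²(N − 1)], given M events among N subjects at the site.

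Percentage of trials flagged, in the order 130×12 / 70 sites / 40×39:

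| Setting | SD | Site-variance test | Treatment-by-site test |
|---|---|---|---|
| No heterogeneity | 0 | 16.0 / 15.3 / 15.0 | 15.3 / 14.5 / 14.6 |
| Risk differs, common effect | 0.3 | 30.3 / 37.7 / 43.1 | 15.2 / 15.2 / 15.4 |
| | 0.5 | 60.2 / 74.1 / 80.5 | 15.6 / 15.1 / 15.2 |
| | 0.7 | 88.6 / 94.7 / 96.7 | 16.1 / 15.9 / 15.5 |
| Effect differs, each site's overall rate held at 6.5% | 0.5 | 14.7 / 14.1 / 14.5 | 24.2 / 28.2 / 31.8 |
| | 0.7 | 13.6 / 14.7 / 14.1 | 32.5 / 40.6 / 45.2 |
| | 1.0 | 12.7 / 12.5 / 12.9 | 48.2 / 62.5 / 71.0 |
| Only BuMA-arm rates differ | 0.5 | 34.1 / 44.6 / 48.9 | 22.8 / 28.4 / 32.2 |
| | 0.7 | 53.6 / 67.2 / 74.0 | 32.8 / 43.0 / 48.7 |
| | 1.0 | 79.6 / 89.8 / 93.0 | 55.0 / 68.9 / 74.3 |

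SDs are on the log-odds scale (rows 2–4 and the last three) or the log odds ratio scale (the three effect rows). Simulation error is at most √(0.25/4000) = 0.8 percentage points. These layouts do not merge small sites by region. A separate simulation that did (130 sites of uneven size) gave similar figures for the planned test: about 30%, 60% and 90% for risk SD 0.3, 0.5 and 0.7; about 16% and 15% for effect SD 0.5 and 0.7 with similar average site rates; and about 61% when only BuMA-arm rates varied with SD 0.7.

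**The case against.** The strongest reply starts from what the test triggers. A significant result does not forbid pooling. It leads to by-site results and a site-stratified analysis, an ordinary response to differing site risk in a trial randomised by site. Non-zero site variance is also heterogeneity in a literal sense. A reader might infer that a flag would block the pooled conclusion; the documents do not say so. This part stands. What remains is that the check is introduced as a test of whether pooling is appropriate, and risk differences do not answer that.

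Second, a reader might infer that the planned test always misses a varying effect. It does not. It stays at its nominal level only when arm rates shift in opposite directions so that each site's overall rate holds. When only BuMA-arm rates vary, it flags more often than the treatment-by-site test (54–74% against 33–49% at SD 0.7). It cannot say which cause it has found, though the by-site display would allow some inspection.

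Third, the alternative has limited power. A log odds ratio SD of 0.7 means that 95% of site odds ratios lie between exp(−1.96×0.7) = 0.25 and exp(1.96×0.7) = 3.9, yet it is flagged in only 33–45% of trials when overall site rates are fixed. This stands and limits what any site check can show here.

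Fourth, the region interaction test, the interaction p-values for five subgroups (Protocol 11.4.6, SAP 5.4) and the 10% enrolment cap per site give partial cover. None of them tests variation between sites.

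Finally, the statement that a non-significant result supports pooling is written for regions only. For sites it is implied by how the check is introduced, not stated.

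**Conclusion.** The concern holds as a minor correction to a supportive check. The site test measures differences in TLF risk. Under the assumed layouts and log-odds SDs of 0.3 to 0.7, such differences alone would trigger the site-stratified analysis in about 30–97% of trials. A non-significant result does not show a consistent device effect: the flag rate is about 13–15% when effects vary and overall site rates do not, and 34–93% when only BuMA-arm rates vary, where the cause cannot be separated from risk.

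The percentages rest on assumed site layouts and SDs, and on score-type stand-ins for the mixed-model tests; the documents give neither the layouts nor the SDs, and 130 sites is an upper limit. The mismatch in what is tested does not depend on them.

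A reader might go further and infer that the primary result is biased or its type I error inflated. Nothing in the documents supports that: the non-inferiority criterion does not depend on this check, and the default pooled test remains valid. One practical gap adds weight. Neither document says how the Farrington-Manning test would be stratified across sites with, at 130 sites, under one expected event each.

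**What to change.** In Protocol 11.4.9 and SAP 5.5:
- After the planned pooling of sites with fewer than 10 subjects, fit the logistic mixed model with treatment, a random site intercept and a random treatment-by-site effect.
- Base the site-pooling assessment on the treatment-by-site variance at 0.15, reported with its estimate and interval.
- Report the intercept variance descriptively, with no consequence for pooling.
- State that a significant result leads to inspection of by-site treatment effects, parallel to the rule for regions, and that the pooled Farrington-Manning test remains the primary analysis.

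The cost is a few sentences and one extra term in a model already planned, with no new data. The downside is modest power: about 24–71% for log odds ratio SDs of 0.5 to 1.0 with overall site rates fixed. The text should therefore say that a non-significant result is only weak evidence of consistency.

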## 11.5 Measures to Minimize Bias

### 11.5.1 Randomization

Subjects will be randomly assigned to a treatment group in a 2:1 ratio (BuMA DES : DP EES) after eligibility criteria have been confirmed (at the time of the index procedure). Randomization will be stratified by presentation (acute coronary syndrome vs. non-ACS) and diabetes status (subjects with vs. without medically-treated diabetes mellitus) given the influence of clinical presentation and diabetes status on the outcome of subjects with CAD. Randomization will also be stratified by study site to avoid introducing bias as a result of site-specific factors.

### 11.5.2 Blinding

This is a single-blind study. The following individuals will be blinded to the subject's treatment allocation:

- Subject and his/her family members
- Site personnel conducting follow-up evaluations will not have access to randomization eCRFs, and every effort will be made to ensure that medical records use a non-specific term to identify the treatment device (e.g., "DES") to avoid revealing treatment group assignment
- Members of the Clinical Events Committee
- Angiographic Core Laboratory technicians performing the analysis

Un-blinding will occur only after the database has been locked for the analysis of the primary endpoint or to protect subject rights, welfare, or well-being at the request of the DSMC.

If a site investigator determines it is necessary to reveal treatment allocation to the subject as a result of complication or injury, he or she is requested to notify the Sponsor.

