## 7.8 Annual Follow-up at 2, 3, 4, and 5 Years (Telephone Contact/Clinic Visit)

All subjects who received any study stent during the index procedure will be contacted by telephone (or optional in-clinic assessment) annually at 2, 3, 4, and 5 years post-procedure for additional follow-up, to include the following assessments:

- Anginal status (CCS, Braunwald classification of unstable angina, or silent ischemia)
- Current concomitant medication documentation. If DAPT has been interrupted or terminated the stop date (and resumption date, if applicable) and the reason for interruption/termination should be recorded.
- Documentation of any adverse events/ serious adverse events occurring since the previous evaluation. All clinically significant adverse events should be carefully documented by the research staff using the adverse event data forms. In the event of repeat intervention after the index procedure or repeat diagnostic cardiac catheterization (regardless of whether revascularization was performed), procedural angiographic images should be forwarded to the Angiographic Core Laboratory. For all adverse events that represent a potential endpoint event, all relevant medical information (including clinically relevant imaging data, ECG data, and the results of relevant laboratory testing performed as part of the standard of care) should be collected and retained as part of the research file to support adverse event analysis and adjudication.

NOTE: For subjects who underwent a phone follow-up at the 12-month time point for any reason, it is preferable that the 2-year follow-up be conducted as an in-clinic visit. For all other subjects, if a clinic visit occurs as part of the subject's regular medical care during the specified follow-up window, the annual follow-up assessment may be conducted during this visit, and no separate telephone contact is necessary.

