## 8.0 Adverse Events and Serious Adverse Events

In this study, patients should be encouraged to report adverse events (AEs) spontaneously or in response to general, non-directed questioning. Any time during the study, the patient may volunteer information that resembles an adverse event (AE). If it is determined that a clinically significant AE has occurred, the investigator should obtain all the information required to complete the AE CRFs. Non-clinically-significant adverse events will not be required post discharge from the initial study procedure.

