### **10.2 Clinical Events Committee (CEC)**

An independent Clinical Events Committee (CEC) will adjudicate all site-reported adverse events that represent a potential endpoint event in an ongoing fashion during the trial. Relationship of these events to the study device and procedure will also be adjudicated.

The CEC will include cardiologists and/or interventional cardiologists experienced in clinical trials who are otherwise independent of the Sponsor and the conduct of the study. Members will not have scientific, financial or other conflicts of interest related to SINOMED or the Investigators. The CEC will operate and

conduct all meetings and event reviews independent of the Sponsor unless specific expert knowledge regarding the characteristics or function of the study device is requested by the CEC from the Sponsor.

The CEC will meet regularly throughout the study to adjudicate events in an ongoing and timely fashion. The adjudication process, event definitions and required source document materials for each type of event will be pre-specified in the CEC Charter prior to the onset of the trial. The adjudication process will include CEC member review of data collected from all relevant medical records, as well as all imaging studies, associated with an event. All adjudication decisions will be made by the CEC in an independent fashion based upon review of all available medical evidence.

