### 11.3.2 Secondary Powered Endpoint

The powered secondary endpoint of the trial is long-term safety and efficacy, defined as TLF between 12 months and 5 years by landmark analysis. The analysis will be performed when the last enrolled subject has completed his/her 5 year clinical follow-up visit.

We assume:

- Randomization ratio is 2:1 (BuMA DES: DP EES)
- The landmark (between 12 months and 5 years) TLF rate in the Control group = 8% (§11.3.3.2)
- The rate of TLF in the control group at 12 months = 6.5% (§11.3.3.1)
- A constant Hazard Ratio in the Intervention group compared to the Control Group = 0.52
- Loss to follow-up = 5% per year (a standard assumption for contemporary trials of coronary stents)
- $\alpha = 0.05$  (two-sided)

Given these assumptions, the planned study sample size of 1444 evaluable subjects at 1 year (accounting for an estimated 5% loss to follow-up at 1 year, a 6.5% rate of TLF prior to 1 year, and a continued annual loss to follow-up of 5%) will provide approximately 80% power to demonstrate superiority of the BuMA DES to DP EES using the log-rank test.

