**Death**

Classified as cardiac, vascular, or noncardiovascular according to the following ARC definitions. All deaths are considered cardiac unless an unequivocal noncardiac cause can be established. Specifically, any unexpected death even in patients with coexisting potentially fatal noncardiac disease (e.g., cancer, infection) should be classified as cardiac.

- **Cardiac death:** Any death due to proximate cardiac cause (e.g., MI, low-output failure, fatal arrhythmia), unwitnessed death and death of unknown cause, and all procedure-related deaths, including those related to concomitant treatment, will be classified as cardiac death.
- **Vascular death:** Death caused by noncoronary vascular causes, such as cerebrovascular disease, pulmonary embolism, ruptured aortic aneurysm, dissecting aneurysm, or other vascular diseases.

- **Noncardiovascular death:** Any death not covered by the above definitions, such as death caused by infection, malignancy, sepsis, pulmonary causes, accident, suicide, or trauma.

Device deficiency	Inadequacy of a medical device related to its identity, quality, durability, reliability, safety or performance.  NOTE: Device deficiencies include malfunction, use error, and inadequate labeling. They may or may not affect device performance or lead to an adverse event.
Device malfunction	Failure of an investigational medical device to perform in accordance with its intended purpose when used in accordance with the Instructions for Use or protocol.  NOTE: A device malfunction occurs when the device is used in compliance with the Instructions for Use, but does not perform as described in the Instructions for Use.
Device misuse	Any use of the investigational device by an investigator that is contradictory to the application described in the Instructions for Use will be categorized as device misuse. This is a form of Use Error.
Device success	Attainment of <30% residual stenosis of the target lesion measured by QCA using the assigned device, evaluated post-procedure
Epicardial vessel	Defined for the purposes of non-target lesion eligibility as the left anterior descending coronary artery, the left circumflex coronary artery, and the right coronary artery, each including its respective branches
Intention to Treat (ITT) Population	All subjects enrolled in the study, by assigned treatment, regardless of the treatment actually received

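### The only general un-blinding point is the 12-month lock, so blinding of subjects and the CEC is not secured through the powered 12-month-to-5-year superiority endpoint

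*Protocol*

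**What the plan says.** Protocol 11.5.2 calls the study single-blind. It lists the blinded parties as the subject and family, site staff doing follow-up evaluations, CEC members and core-laboratory technicians. The list has no end date. The section then says: "Un-blinding will occur only after the database has been locked for the analysis of the primary endpoint", or at the DSMC's request to protect subjects. It also provides for an investigator telling an individual subject after a complication or injury. The synopsis carries the same rule.

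The powered secondary endpoint, in Protocol 11.4.4, is "defined as TLF between 12 months and 5 years by landmark Kaplan-Meier analysis, will be a test for superiority of the BuMA DES group" over DP EES. On timing, Protocol 11.3.2 says: "The analysis will be performed when the last enrolled subject has completed his/her 5 year clinical follow-up visit".

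Data for this endpoint keep arriving after the 12-month lock:
- Under Protocol 7.8, stented subjects "will be contacted by telephone (or optional in-clinic assessment) annually at 2, 3, 4, and 5 years post-procedure for additional follow-up".
- Under Protocol 8.0, "patients should be encouraged to report adverse events (AEs) spontaneously or in response to general, non-directed questioning".
- Under Protocol 10.2, the CEC "will adjudicate all site-reported adverse events that represent a potential endpoint event in an ongoing fashion during the trial". The adjudication process, definitions and source requirements "for each type of event will be pre-specified in the CEC Charter prior to the onset of the trial".

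The SAP has no blinding section. Its one mention of unblinding (SAP 3.0) says that analysis populations are settled beforehand and gives neither date nor scope.

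**The concern.** The trial has two powered confirmatory hypotheses, and the stated release point serves only the first. The second is a superiority test at two-sided 0.05, and it also gates formal superiority testing of the primary endpoint (Protocol 11.4.8). A team could follow 11.5.2 exactly, un-blind subjects and CEC members once the 12-month data are locked, and then collect and adjudicate most of the superiority endpoint without that protection.

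The events open to influence are those that need judgement:
- a revascularization with 50-69% stenosis that counts as clinically driven because angina is reported;
- attribution of an MI to the target vessel;
- cause of death.

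Knowledge of the stent could affect what a subject reports or how a borderline case is classified. The documents give no basis for saying which arm this would favour.

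**Working it through.** **1. Who is covered after the 12-month lock**

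| Role | What the documents provide | End date |
|---|---|---|
| Subject and family | On the blinded list (11.5.2) | None stated |
| Follow-up site staff | On the list; no access to randomization eCRFs; neutral device term in records (11.5.2) | None stated |
| CEC members | On the list; process set in an unseen Charter (10.2) | None stated |
| Core-laboratory technicians | On the list; described again as blinded in 11.5.3 | None stated |
| Operators | Not on the list | Not applicable |

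No listed role is expressly exempted from the rule that allows un-blinding after the primary-endpoint lock. Follow-up staff and the core laboratory have additional wording that is not tied to the lock. Subjects do not, and for the CEC the Charter would have to be seen.

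**2. The plan's own figures for the secondary endpoint**

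Inputs from Protocol 11.3.2: control landmark TLF 8% over 4 years, hazard ratio 0.52, loss 5% per year, 2:1 allocation, 1444 subjects at 1 year.

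- Subjects at 1 year: 1632 × (1 − 0.05 − 0.065) = 1444.3, which matches 1444. Split 2:1, this is 481.3 control and 962.7 BuMA.
- Annual hazards: control λ = −ln(0.92)/4 = 0.02085; BuMA 0.52 × 0.02085 = 0.01084; loss μ = −ln(0.95) = 0.05129.
- Expected events per arm: N × λ/(λ+μ) × [1 − exp(−4(λ+μ))], giving 34.9 control + 37.0 BuMA = 71.8.
- Power by Freedman's formula: z = √(2 × 71.8) × (1 − 0.52)/(1 + 2 × 0.52) = 2.82; 2.82 − 1.96 = 0.86, or 80.5%. This reproduces the stated figure of approximately 80%. The variance 1/34.9 + 1/37.0 for the log hazard ratio gives 79.1%; Schoenfeld's formula gives 74.3%.

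**3. How much of the endpoint falls after the lock**

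The synopsis gives first enrolment as October 2017 and last as August 2019. The lock date and the accrual pattern are not stated. Assumptions: entry uniform from 1 October 2017 to 31 August 2019; lock between 30 September 2020 and 31 August 2021. The earlier date is 31 August 2019 plus 12 months plus the 30-day visit window, because SAP 4.0 waits for completed visits or the end of the window.

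Let a be the landmark years already elapsed for a subject at the lock, between 0 and 4. The share of window time after the lock is 1 − mean(a)/4. Events after the lock are the mean over entry dates of N × λ/(λ+μ) × [exp(−(λ+μ)a) − exp(−4(λ+μ))], summed over arms.

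| Lock date | Mean a (years) | Window after lock | Events after lock (control + BuMA) |
|---|---|---|---|
| 30 Sep 2020 | 1.04 | 74.0% | 24.9 + 26.5 = 51.4 |
| 31 Dec 2020 | 1.29 | 67.7% | 22.6 + 24.1 = 46.7 |
| 28 Feb 2021 | 1.45 | 63.6% | 21.1 + 22.5 = 43.6 |
| 31 Aug 2021 | 1.96 | 51.0% | 16.6 + 17.8 = 34.4 |

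As shares of 71.8, the extremes are 72% and 48% of expected events. If accrual density falls or rises linearly instead, the range over the same lock dates widens to 43-82% of the window and 29-58 events.

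These counts cover every TLF event. The documents do not give the fraction that turns on judgement, so no count of vulnerable events is offered.

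**The case against.** The strongest reply is that the protocol is silent on an end date and plans no un-blinding at 12 months. Blinding with no end date can be read as continuing until someone is actually un-blinded. That is a fair reading, and a reader who inferred that the plan orders un-blinding at the lock would be wrong. What remains is that the only release point given is the 12-month one, so un-blinding then would comply with the protocol.

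A reader might also infer that follow-up staff and the core laboratory lose all protection at the lock. The documents do not support that. The eCRF restriction and the neutral device term (11.5.2), and the description of technicians as blinded (11.5.3), have no time limit.

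Nor is the endpoint scored by telephone. Calls detect events. Protocol 7.8 then requires supporting records and sends films to the core laboratory, and Protocol 10.2 has the CEC review records and imaging.

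The definitions in Appendix A narrow the room for bias further. Core-laboratory QCA prevails on stenosis, and 70% or more needs no symptom. Investigators should classify a TLR as clinically driven or not before angiography. An MI counts as target-vessel unless clearly attributable elsewhere. For deaths, "All deaths are considered cardiac unless an unequivocal noncardiac cause can be established". Operators know the stent throughout, and extended blinding would not change that.

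All of this stands as mitigation. None of it states how long subjects or the CEC remain blinded.

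**Conclusion.** The point holds as a gap in the blinding rule. Un-blinding of subjects, and of the CEC unless its Charter prevents it, is permitted from the 12-month lock, while the powered superiority endpoint still has about 51-74% of its observation window and 34-51 of about 72 expected events to come. Those ranges rest on uniform accrual over the anticipated enrolment dates, a lock between 30 September 2020 and 31 August 2021, and the event, hazard-ratio and loss assumptions in Protocol 11.3.2.

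They measure exposure only. A reader might infer that the secondary test is biased or its type I error inflated. The documents do not support that: no passage plans the un-blinding, the direction of any effect is unknown, and no effect on the hazard ratio can be estimated. Confidence is medium, mainly because the CEC Charter was not available. The change is worth making because it is a specific, low-cost protection for a confirmatory test.

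**What to change.** Add to Protocol 11.5.2, the synopsis and the SAP: after the database lock for the 12-month primary endpoint, subjects and their families, site personnel conducting follow-up evaluations, CEC members and Angiographic Core Laboratory technicians remain blinded to individual treatment assignment until the database is locked for the 5-year analysis. Keep the existing exceptions (DSMC request; investigator disclosure for complication or injury). Align the CEC Charter. No new restriction on the Sponsor is needed.

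The text change is small, but it is a protocol amendment. Protocol 15.7 requires approval by the Sponsor, the Principal Investigators, the IRB/EC and any necessary regulatory body, at up to 130 sites in three regions. Subjects would learn their stent type later. The 12-month report, including the subject-level 1-year listings in SAP 7.1, must not reveal individual assignment to the blinded roles. Sample size and analysis are unchanged, and operators remain un-blinded.
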